^{bb} After informed consent has been obtained but prior to initiation of study drug, only serious adverse events caused by a protocol-mandated intervention should be reported. After initiation of study drug, all adverse events will be reported until 5 months after the final dose of study drug. After this period, all deaths, regardless of cause, should be reported. In addition, the Sponsor should be notified if the investigator becomes aware of any serious adverse event that is believed to be related to prior study drug treatment.

^{cc} The DCL will be assessed at screening only (i.e., without the full TMS assessment). The TMS scale will be assessed (excluding the DCL) at all other timepoints.

^{dd} Excluding MRIs, which have a visit window of -14 to -7 days.

^{ee} *Telephone safety follow-up calls will assess any changes to ongoing adverse events or occurrence of new adverse events and changes to concomitant medication. Unscheduled visits can occur based on the outcome of this safety follow-up call.*

Appendix 2 Clinician-Reported Outcomes for Patients Enrolled after Implementation of Protocol Version 4

Assessment	Name	Items	Concepts	Approx. Duration	Timing
FA	UHDRS Functional Assessment	25	Daily function	15 min	Baseline and Weeks 5, 21, 37, 53, 69, 85, and 101 and ETT visits
IS	Independence Scale	1	Functional disability	3 min	Screening, baseline, and Weeks 5, 21, 37, 53, 69, 85, and 101 and ETT visits
TFC	Total Functional Capacity Scale	5	Overall function	10 min	Baseline and Weeks 5, 21, 37, 53, 69, 85, and 101 and ETT visits
TMS	Total Motor Score	31	Motor function	15 min	DCL only: Screening TMS without DCL: Baseline and Weeks 5, 21, 37, 53, 69, 85, and 101 and ETT visits
C-SSRS	Columbia-Suicide Severity Scale	5	Suicidal ideation and behavior	20 min full version; 5 min follow-up version	Full version at screening in clinic; follow-up version at baseline and all post-baseline clinic visits
CGI-S	Clinical Global Impression, Severity	1	Overall severity of patient status	2 min	Baseline and Weeks 5, 21, 37, 53, 69, 85, and 101 and ETT visits
CGI-C	Clinical Global Impression, Change	1	Overall change in patient status	2 min	Weeks 5, 21, 37, 53, 69, 85, and 101 and ETT visits
HD-DAS	Huntington's Disease Daily Activities Scale	25	Daily function	25 min	Screening and Weeks 13, 29, 45, 61, 77, and 93

DCL=diagnostic confidence level.

Appendix 3 Patient-Reported, Observer-Reported, and Performance Outcomes and Roche HD Mobile Application for Patients Enrolled after Implementation of Protocol Version 4

Assessment	Name	Items	Concepts	Approx. Duration (min)	PRO, ObsRO, PerfO, Behavior	Timing	Location
AES	Apathy Evaluation Scale	18	Apathy	10	PRO+ObsRO	Baseline and Weeks 13, 29, 45, 61, 77, 93, and 101	In-clinic
Roche HD mobile app	Roche HD mobile app with daily Active Test and Passive Monitoring	NA	Tasks (“active test”) that assess motor symptoms (upper and lower body movements, upper limb dexterity, voice) and non-motor symptoms (processing speed/voice); continuous passive monitoring	5	Sensor data, PRO, PerfO	Daily+at clinic visits (Screening, baseline and Weeks 5, 53, and 101 and ETT visits)	Roche HD mobile app
CrGI-C	Companion-Reported Global Impression, Change	1	Overall change in patient status	2	ObsRO	Weeks 5, 21, 37, 53, 69, 85, and 101 and ETT visits	In-clinic on electronic device
CrGI-S	Companion-Reported Global Impression, Severity	1	Overall severity of patient status	2	ObsRO	Baseline and Weeks 5, 21, 37, 53, 69, 85, and 101 and ETT visits	In-clinic on electronic device
EQ-5D-5L	EuroQol 5-Dimension, 5-Level Questionnaire	6	Health utilities	5	PRO+ObsRO	Baseline and Weeks 5, 21, 37, 53, 69, 85, and 101 and ETT visits	In-clinic
						Weekly	Roche HD mobile app; electronic device

Appendix 3:Patient-Reported, Observer-Reported, and Performance Outcomes and Roche HD Mobile Application for Patients Enrolled after Implementation of Protocol Version 4 (cont.)

Assessment	Name	Items	Concepts	Approx. Duration (min)	PRO, ObsRO, PerfO, Behavior	Timing	Location
HD-SDI	Huntington's Disease Speaking Difficulty Item	1	Speech	1	PRO	Weekly	Roche HD mobile app
HD-CIAOS	Huntington's Disease Companion-Reported Irritability and Angry Outbursts Scale	3	Irritability and angry outbursts	2	ObsRO	Weekly	Electronic device
HUI®	Health Utilities Index	15	Health-related quality of life	10	ObsRO	Baseline, Weeks 5, 21, 37, 53, 69, 85, and 101 and ETT	In-clinic
						Weekly	Electronic device
MoCA	Montreal Cognitive Assessment	11	Overall cognitive status	10	PerfO	Screening, baseline, Weeks 5, 21, 37, 53, 69, 85, and 101 and ETT	In-clinic
Neuro-QoL Cog Func	Neuro-QoL Cognitive Function Short Form	8	Cognition	5	PRO	Baseline and Weeks 5, 21, 37, 53, 69, 85, and 101	In-clinic
PGI-C	Patient Global Impression, Change	1	Overall change in patient status	2	PRO	Weeks 5, 21, 37, 53, 69, 85, and 101 and ETT visits	In-clinic
PGI-S	Patient Global Impression, Severity	1	Overall severity of patient status	2	PRO	Baseline and Weeks 5, 21, 37, 53, 69, 85, and 101 and ETT	In-clinic

Appendix 3: Patient-Reported, Observer-Reported, and Performance Outcomes and Roche HD Mobile Application for Patients Enrolled after Implementation of Protocol Version 4 (cont.)

Assessment	Name	Items	Concepts	Approx. Duration (min)	PRO, ObsRO, PerfO, Behavior	Timing	Location
SDMT/ eSDMT	Symbol Digit Modalities Test	Max number in 90 seconds	Cognitive	5	PerfO	SDMT at baseline and Weeks 5, 21, 37, 53, 69, 85, and 101 and ETT visits	In-clinic
						eSDMT monthly + at clinic visits (screening, baseline, Weeks 5, 53, 101, and ETT)	Roche HD mobile app (eSDMT)
SMDDS	Symptoms of Major Depressive Disorder Scale	16	Depression, anxiety, irritability, sleep	10	PRO	Baseline and Weeks 13, 29, 45, 61, 77, 93, and 101	In-clinic
SWR/eSWR	Stroop Word Reading Test	Max numbers in 45 seconds	Cognitive	5	PerfO	SWR at baseline and Weeks 5, 21, 37, 53, 69, 85, and 101 and ETT visits	In-clinic
						eSWR monthly + at clinic visits (screening, baseline, Weeks 5, 53, and 101 and ETT)	Roche HD mobile app (eSWR)
WPAI	Work Productivity and Activity Impairment	6	Work productivity	5	PRO+ObsRO	Baseline and then monthly	Roche HD mobile app and electronic device

app = application; ETT = early treatment termination; HD = Huntington disease; ObsRO = observer-reported outcome; PerfO = performance outcome; PRO = patient-reported outcome.

Appendix 4 Clinical Assessments Order and Duration for Patients Enrolled after Implementation of Protocol Version 4

Table 1 Screening Visit Clinical Assessments

Block	Assessments	Total Duration (minutes)	Site Staff Responsible
1	Diagnostic Confidence Level Huntington's Disease Daily Activities Scale Independence Scale MoCA C-SSRS	~60	Qualified study physician
Break (if needed)		~20-30	
2	Roche HD mobile application	~20	Qualified study personnel

C-SSR=Columbia-Suicide Severity Rating Scale; HD=Huntington disease; MoCA=Montreal Cognitive Assessment.

Appendix 4: Clinical Assessments Order and Duration for Patients Enrolled after Implementation of Protocol Version 4 (cont.)

Table 2 Baseline and Week 101 Clinical Assessments (for Primary Analysis)

Block	Assessments	Total Duration (minutes)	Site Staff Responsible
1	UHDRS Functional Assessment Independence Scale Total Functional Capacity Scale Total Motor Score (without Diagnostic Confidence Level) Columbia-Suicide Severity Rating Scale Clinical Global Impression—Severity Clinical Global Impression—Change (post-baseline visits only)	~60	Qualified study physician
	Break (if needed)	~20–30	
2	Symbol Digit Modalities Test Stroop Word Reading Test MoCA	~20	Qualified study personnel
	Break (if needed)	~10	
3 ^a	Apathy Evaluation Scale (patient and companion) Symptoms of Major Depressive Disorder Scale	~20	Qualified study personnel
	Break (if needed)	~10–20	
4 ^a	Neuro-QoL Cognition Function Short Form EuroQol 5-Dimension, 5-Level Questionnaire (patient and companion) Health Utilities Index (companion: self and proxy) Patient/Companion-reported Global Impression—Severity Patient/Companion-reported Global Impression—Change (post-baseline visits only)	~20	Qualified study personnel
	Break (if needed)	~10–20	
5 ^a	Roche HD mobile application	~20	Qualified study personnel

HD=Huntington disease; MoCA=Montreal Cognitive Assessment; Neuro-QoL=Quality of Life in Neurological Disorders; UHDRS=Unified Huntington's Disease Rating Scale.

^a At the baseline visit and at week 101, Blocks 3, 4, and 5 can be completed on the same day after Blocks 1 and 2, or on the following day, but must be completed predose at the baseline visit.

Appendix 4: Clinical Assessments Order and Duration for Patients Enrolled after Implementation of Protocol Version 4 (cont.)

Table 3 Follow-Up Clinical Assessments at Weeks 5, 21, 37, 53, 69, and 85

Block	Assessments	Total Duration (minutes)	Site Staff Responsible
1	UHDRS Functional Assessment Independence Scale Total Functional Capacity Scale Total Motor Score (without Diagnostic Confidence Level) Columbia-Suicide Severity Rating Scale Clinical Global Impression—Severity Clinical Global Impression—Change	~60	Qualified study physician
	Break (if needed)	~20-30	
2	Symbol Digit Modalities Test Stroop Word Reading Test MoCA	~20	Qualified study personnel
	Break (if needed)	~10	
3	Neuro-QoL Cognition Function Short Form EuroQol 5-Dimension, 5-Level Questionnaire (patient and companion) Health Utilities Index (companion: self and proxy) Patient/Companion-reported Global Impression—Severity Patient/Companion-reported Global Impression—Change	~30	Qualified study personnel
4	Roche HD mobile application ^a	~20	Qualified study personnel

MoCA=Montreal Cognitive Assessment; Neuro-QoL=Quality of Life in Neurological Disorders;
UHDRS=Unified Huntington's Disease Rating Scale

^a These assessments will take place only at Weeks 5 and 53.

Appendix 4: Clinical Assessments Order and Duration for Patients Enrolled after Implementation of Protocol Version 4 (cont.)

Table 4 Follow-Up Clinical Assessments at Weeks 13, 29, 45, 61, 77, and 93

Block	Assessments	Total Duration (minutes)	Site Staff Responsible
1 ^a	Apathy Evaluation Scale (patient and companion) Symptoms of Major Depressive Disorder Scale	~20	Qualified study personnel
	Break (if needed)	~10	
2	Huntington's Disease-Daily Activities Scale	~25	Qualified study physician

^a To be completed prior to safety assessments.

Appendix 5 Grading Scale for Adverse Events Relating to Laboratory Abnormalities for All Patients

The following grading recommendations for adverse events relating to lab test abnormalities are based on the National Cancer Institute Common Terminology Criteria for Adverse Events, Version 5.0.

Adverse Event	Mild	Moderate	Severe
Hematology			
aPTT prolonged	>ULN - 1.5 x ULN	>1.5 - 2.5 x ULN	>2.5 x ULN; hemorrhage
Eosinophils increased ¹	650 - 1,500 cell/mm ³	1,501 - 5,000 cell/mm ³	>5,000 cell/mm ³
Fibrinogen decreased	<1.0 - 0.75 x LLN or <25% decrease from baseline	<0.75 - 0.5 x LLN or 25 - <50% decrease from baseline	<0.5 x LLN or ≥50% decrease from baseline
Hemoglobin decreased (Anemia)	Hemoglobin (Hgb) <LLN - 10.0 g/dL; <LLN - 6.2 mmol/L; <LLN - 100 g/L	Hgb <10.0 - 8.0 g/dL; <6.2 - 4.9 mmol/L; <100 - 80 g/L	Hgb <8.0 g/dL; <4.9 mmol/L; <80 g/L; transfusion indicated
Hemoglobin increased	Increase in >0 - 2 g/dL above ULN or above baseline if baseline is above ULN	Increase in >2 - 4 g/dL above ULN or above baseline if baseline is above ULN	Increase in >4 g/dL above ULN or above baseline if baseline is above ULN
INR increased	>1 - 1.5 x ULN; >1 - 1.5 times above baseline if on anticoagulation	>1.5 - 2.5 x ULN; >1.5 - 2.5 times above baseline if on anticoagulation	>2.5 x ULN; >2.5 times above baseline if on anticoagulation
Lymphocyte count decreased	<LLN - 800/mm ³ ; <LLN - 0.8 x 10 ⁹ /L	<800 - 500/mm ³ ; <0.8 - 0.5 x 10 ⁹ /L	<500 /mm ³ ; <0.5 x 10 ⁹ /L
Lymphocyte count increased	-	>4000/mm ³ - 20,000/mm ³	>20,000/mm ³
Neutrophil count decreased	<LLN - 1500/mm ³ ; <LLN - 1.5 x 10 ⁹ /L	<1500 - 1000/mm ³ ; <1.5 - 1.0 x 10 ⁹ /L	<1000/mm ³ ; <1.0 x 10 ⁹ /L
Platelet count decreased	<LLN - 75,000/mm ³ ; <LLN - 75.0 x 10 ⁹ /L	<75,000 - 50,000/mm ³ ; <75.0 - 50.0 x 10 ⁹ /L	<50,000/mm ³ ; <50.0 x 10 ⁹ /L
White blood cell decreased	<LLN - 3000/mm ³ ; <LLN - 3.0 x 10 ⁹ /L	<3000 - 2000/mm ³ ; <3.0 - 2.0 x 10 ⁹ /L	<2000/mm ³ ; <2.0 x 10 ⁹ /L
Chemistry			
Acidosis	pH <normal, but >=7.3	-	pH <7.3
Alanine aminotransferase increased	>ULN - 3.0 x ULN	>3.0 - 5.0 x ULN	>5.0 x ULN
Alkaline phosphatase increased	>ULN - 2.5 x ULN	>2.5 - 5.0 x ULN	>5.0 x ULN
Alkalosis	pH >normal, but ≤7.5	-	pH >7.5
Aspartate aminotransferase increased	>ULN - 3.0 x ULN	>3.0 - 5.0 x ULN	>5.0 x ULN
Blood bilirubin increased	>ULN - 1.5 x ULN	>1.5 - 3.0 x ULN	>3.0 x ULN
Cardiac troponin I increased	Levels above the upper limit of normal and below the level of myocardial infarction as defined by the manufacturer	-	Levels consistent with myocardial infarction as defined by the manufacturer

LLN=lower limit of normal; ULN=upper limit of normal.

Appendix 5: Grading Scale for Adverse Events Relating to Laboratory Abnormalities for All Patients (cont.)

Adverse Event	Mild	Moderate	Severe
Cardiac troponin T increased	Levels above the upper limit of normal and below the level of myocardial infarction as defined by the manufacturer	-	Levels consistent with myocardial infarction as defined by the manufacturer
CD4 lymphocytes decreased	<LLN - 500/mm ³ ; <LLN - 0.5 x 10 ⁹ /L	<500 - 200/mm ³ ; <0.5 - 0.2 x 10 ⁹ /L	<200/mm ³ ; <0.2 x 10 ⁹ /L
CPK increased*	>ULN - <6 ULN	6 - 10 x ULN	>10 x ULN
Creatinine increased	>1 - 1.5 x baseline; >ULN - 1.5 x ULN	>1.5 - 3.0 x baseline; >1.5 - 3.0 x ULN	>3.0 x baseline; >3.0 x ULN
GGT increased	>ULN - 2.5 x ULN	>2.5 - 5.0 x ULN	>5.0 x ULN
Hypercalcemia	Corrected serum calcium of >ULN - 11.5 mg/dL; >ULN - 2.9 mmol/L; Ionized calcium >ULN - 1.5 mmol/L	Corrected serum calcium of >11.5 - 12.5 mg/dL; >2.9 - 3.1 mmol/L; Ionized calcium >1.5 - 1.6 mmol/L; symptomatic	Corrected serum calcium of >12.5 mg/dL; >3.1 mmol/L; Ionized calcium >1.6 mmol/L; hospitalization indicated
Hyperglycemia	Fasting glucose value >ULN - 160 mg/dL; Fasting glucose value >ULN - 8.9 mmol/L	Fasting glucose value >160 - 250 mg/dL; Fasting glucose value >8.9 - 13.9 mmol/L	>250 mg/dL; >13.9 mmol/L; hospitalization indicated
Hyperkalemia	>ULN - 5.5 mmol/L	>5.5 - 6.0 mmol/L	>6.0; hospitalization indicated
Hypermagnesemia	>ULN - 3.0 mg/dL; >ULN - 1.23 mmol/L	-	>3.0 mg/dL; >1.23 mmol/L
Hypernatremia	>ULN - 150 mmol/L	>150 - 155 mmol/L	>155 mmol/L; hospitalization indicated
Hyperuricemia	>ULN - 10 mg/dL (0.59 mmol/L) without physiologic consequences	-	>ULN - 10 mg/dL (0.59 mmol/L) with physiologic consequences
Hypoalbuminemia	<LLN - 3 g/dL; <LLN - 30 g/L	<3 - 2 g/dL; <30 - 20 g/L	<2 g/dL; <20 g/L
Hypocalcemia	Corrected serum calcium of <LLN - 8.0 mg/dL; <LLN - 2.0 mmol/L; Ionized calcium <LLN - 1.0 mmol/L	Corrected serum calcium of <8.0 - 7.0 mg/dL; <2.0 - 1.75 mmol/L; Ionized calcium <1.0 - 0.9 mmol/L; symptomatic	Corrected serum calcium of <7.0 mg/dL; <1.75 mmol/L; Ionized calcium <0.9 mmol/L; hospitalization indicated
Hypoglycemia	<LLN - 55 mg/dL; <LLN - 3.0 mmol/L	<55 mg/dL; <3.0 mmol/L	<40 mg/dL (<2.2 mmol/L) AND requires assistance of another person to actively administer carbohydrates, glucagon, or take other corrective actions ^t
Hypokalemia	<LLN - 3.0 mmol/L	<LLN - 3.0 mmol/L; symptomatic; intervention indicated	<3.0 mmol/L; hospitalization indicated
Hypomagnesemia	<LLN - 1.2 mg/dL; <LLN - 0.5 mmol/L	<1.2 - 0.9 mg/dL; <0.5 - 0.4 mmol/L	<0.9 mg/dL; <0.4 mmol/L
Hyponatremia	<LLN - 130 mmol/L	-	<130 mmol/L
Hypophosphatemia	<LLN - 2.5 mg/dL; <LLN - 0.8 mmol/L	<2.5 - 2.0 mg/dL; <0.8 - 0.6 mmol/L	<2.0 mg/dL; <0.6 mmol/L
Lipase increased	>ULN - 1.5 x ULN	>1.5 - 2.0 x ULN	>2.0 x ULN
Serum amylase increased	>ULN - 1.5 x ULN	>1.5 - 2.0 x ULN	>2.0 x ULN

LLN = lower limit of normal; ULN = upper limit of normal.

Appendix 5: Grading Scale for Adverse Events Relating to Laboratory Abnormalities for All Patients (cont.)

Adverse Event	Mild	Moderate	Severe
Urine			
Proteinuria			
Adults	1+ proteinuria; urinary protein <1.0 g/24 hrs	2+ proteinuria; urinary protein 1.0 - 3.4 g/24 hrs; Urine P/C (Protein/Creatinine) ratio 0.5 - 1.9	Urinary protein ≥3.5 g/24 hrs; Urine P/C >1.9
Children	-		
Hematuria	Asymptomatic; clinical or diagnostic observations only; intervention not indicated	Symptomatic; urinary catheter or bladder irrigation indicated	Gross hematuria; transfusion, IV medications or hospitalization indicated; elective endoscopic, radiologic or operative intervention indicated

[†]Grading for this parameter is derived from the Toxicity Grading Scale for Healthy Adult and Adolescent Volunteers Enrolled in Preventive Vaccine Clinical Trials, Sept 2007

^{*}Grading for this parameter is derived from the Division of AIDS (DAIDS) Table for Grading the Severity of Adult and Pediatric Adverse Events Version 2.0, Nov 2014

[‡]Modified for consistency with the ADA and Endocrine Society Guidelines (Sequist ER, Anderson J, Childs B, et al. Hypoglycemia and Diabetes: A Report of a Workgroup of the American Diabetes Association and The Endocrine Society. Diabetes Care 2013;36:1384-95)

Appendix 6 Roche HD Mobile Application for Patients Enrolled after Implementation of Protocol Version 4: Active Test

The following tasks are part of the "active tests" conducted on the Roche Huntington's Disease (HD) mobile application by the patient.

Daily Questions

Two daily single-item questions on mood and physical energy will be assessed, asking patients about their mood and physical health at the time they are performing the "Active" tests. The assessments aim to capture daily mood fluctuations and will be used as a control for the other motor and cognitive assessments.

Cognitive Test (eSDMT)

The Cognitive Test asks participants to match symbols with numbers according to a key as quickly and accurately as possible. The key, symbols, numbers are all displayed on a smartphone screen. The test assesses visuo-motor integration, and measures visual attention and motor speed. It is modelled on the pen and paper Symbol Digit Modalities Test (SDMT) (Smith, 1968). The SDMT has been shown to be sensitive to symptom changes in early HD patients (Tabrizi 2012) and is part of the Unified Huntington's Disease Rating Scale (UHDRS) assessment (Huntington's Study Group, 1996).

Word Reading Test (eSWR)

The Word Reading Test asks participants to read aloud color words written in black font on a smartphone screen. Their voice will be recorded. The test assesses cognitive processing speed, and is modelled on the Stroop Word Reading (SWR) (Ridley 1935). The "Word Reading" part of the SWR Test has been shown to be sensitive to symptom changes in patients with early HD (Tabrizi 2012) and is part of the UHDRS assessment (Huntington's Study Group 1996).

Speeded Tapping Test

The Speeded Tapping Test asks participants to tap the smartphone screen as fast and regularly as possible, using the index finger of both the left and right hands. The test assesses bradykinesia. Performance will also be impacted by chorea and dystonia. It is modelled on tapping tests shown to be sensitive to symptom changes in early HD (Bechtel et al. 2010; Tabrizi et al. 2012). A similar finger tapping task is also included as part of the UHDRS assessment (Huntington's Study Group 1996).

Draw a Shape Test

The Draw a Shape Test asks participants to trace a series of increasingly complex shapes on the smartphone screen. The shapes include lines, a square, a circle, an eight, and a spiral. This test is designed to assess visuomotor coordination and fine motor impairment in early HD patients. It is modelled on circle tracing tasks that have been shown to be sensitive to symptom changes in early HD (Say et al. 2011; Tabrizi et al. 2013).

Chorea Test

The Chorea Test asks participants to hold the smartphone still in their hand with their arm outstretched, and wear the wrist-worn wearable. As a dual task, participants will also need to count backwards aloud. To ensure correct execution, voice will be recorded. The test is designed to assess chorea. It draws on other sensor-based approaches to measure chorea (Reilmann et al. 2010, 2011; Kegelmeyer et al. 2017). A chorea assessment is also part of the UHDRS (Huntington's Study Group 1996).

Balance Test

The Balance Test asks participants to stand still while wearing the smartphone and wrist-worn wearable. It is an assessment for patients' static balance function. Sensor-based approaches for

Appendix 6: Roche HD Mobile Application for Patients Enrolled after Implementation of Protocol Version 4: Active Test (cont.)

measuring static balance have been shown to be sensitive to differences in symptoms in early HD (Dalton et al. 2013). The test is also part of established scales like the Berg Balance Scale (Berg et al. 1992), which are used in HD (Busse et al. 2009; Rao et al. 2009). The test is anchored to the UHDRS assessments for maximal dystonia, maximal chorea, and tandem walking (Huntington Study Group 1996).

U-Turn Test

The U-Turn Test asks participants to walk and turn safely between two points that are at least four steps apart, while wearing the smartphone and wrist-worn wearable. They need to make at least five turns. The test is designed to assess gait and lower-body bradykinesia, which are also assessed by the UHDRS. It is modelled on the Timed Up and Go Test, which has been clinically validated for the HD population (Busse et al. 2009; Rao et al. 2009). The test is anchored to the UHDRS gait, bradykinesia body, and tandem walking items (Huntington Study Group 1996).

Walk Test

The Walk Test asks participants walk as fast as is safely possible for 200 meters or 2 minutes every day. Ideally, the test is done in a straight path with no obstacles (e.g., in a park). Sensor-based approaches for measuring gait have been shown to be sensitive to differences in symptoms in early HD (Dalton et al. 2013). The test is anchored to the UHDRS gait, bradykinesia body, and tandem walking items (Huntington Study Group 1996).

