4.5.6 Laboratory, Biomarker, and Other Biological Samples

Samples for the following laboratory tests will be sent to the study site's local laboratory for analysis:

- Coagulation: INR *and/or* PT, aPTT, and platelet count
- Urine pregnancy test

Urine pregnancy tests will be performed for women of childbearing potential at specified visits. If a urine pregnancy test is positive, it must be confirmed by a serum pregnancy test (analyzed at a central laboratory).

- CSF for safety: cell count (*including* RBCs and WBCs), glucose, and protein
- CSF sample for differential cell counts (*absolute or percentage*), where feasible

The following samples will be sent to a central laboratory:

- Hematology: WBC count, RBC count, platelet count, hemoglobin, hematocrit, and differential count (neutrophils, eosinophils, basophils, monocytes, lymphocytes)
- Serum chemistry panel: bicarbonate or total carbon dioxide (if considered standard of care for the region), sodium, potassium, chloride, glucose, BUN or urea, creatinine, total protein, albumin, phosphorus, calcium, total and direct bilirubin, ALP, ALT, AST, uric acid, gamma-glutamyl transferase, and CPK
- Thyroid panel: thyroid-stimulating hormone and free thyroxine (also known as T4) levels
- Viral serology: HBsAg and HCV antibody
- Serum pregnancy test

Serum pregnancy tests will be performed for women of childbearing potential at screening. *At subsequent visits, it will be performed to confirm a positive urine pregnancy test (if applicable).*

- Urinalysis, including dipstick (pH, specific gravity, glucose, protein, ketones, blood) and microscopic examination *for all abnormal dipstick results* (sediment, RBCs, WBCs, casts, crystals, epithelial cells, bacteria)
- CSF and blood (plasma) samples for PK analyses and metabolite identification
- Blood (plasma) samples for immunogenicity analyses
- Blood sample for determination of CAG repeat length in *HTT* for patient eligibility
- CSF samples for analysis of mHTT and NfL levels to evaluate the effects of RO7234292 compared with placebo (primary and secondary biomarker endpoints)
- Blood, plasma, and CSF samples for exploratory research on biomarkers and biomarker assay development

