5.3.3 Assessment of Severity of Adverse Events

The adverse event severity grading scale indicated in Table 4 will be used for assessing adverse event severity. Laboratory values determined as an adverse event should be graded as per Appendix 5, which is based on the NCI CTCAE (v5.0).

Table 4 Adverse Event Severity Grading Scale

Severity	Description
Mild	Discomfort noticed, but no disruption of normal daily activity
Moderate	Discomfort sufficient to reduce or affect normal daily activity
Severe	Incapacitating with inability to work or to perform normal daily activity

Note: Regardless of severity, some events may also meet seriousness criteria.
Refer to definition of a serious adverse event (see Section 5.2.2).

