- ^m Serum chemistry panel: includes bicarbonate or total carbon dioxide (if considered standard of care for the region), sodium, potassium, chloride, glucose, BUN or urea, creatinine, total protein, albumin, phosphorus, calcium, total and direct bilirubin, ALP, ALT, AST, uric acid, gamma-glutamyl transferase, and CPK.
- ⁿ All women of childbearing potential will have a serum pregnancy test at screening. Urine pregnancy tests will be performed at specified subsequent visits. If a urine pregnancy test is positive, it must be confirmed by a serum pregnancy test.
- ^o Urinalysis includes dipstick (pH, specific gravity, glucose, protein, ketones, blood) and microscopic examination *for all abnormal dipstick results* (sediment, RBCs, WBCs, casts, crystals, epithelial cells, bacteria).
- ^p At the Week 37 visit, PK samples will be collected prior to dosing and at 1, 2, and 4 hours post-dose. All patients will remain in clinic at least 4 hours after lumbar puncture.
- ^q *MRI should take place as early as possible within the screening window but may take place at any time during screening. The MRI safety and efficacy screening scan will need to pass the central laboratory image QC and the results must be available before the patient can be enrolled in the study. At Weeks 13, 37, 69, 101 and at the EoT for ETT visit the MRI should be scheduled to occur before the lumbar puncture.*

Appendix 1: Schedule of Activities for Patients Enrolled after Implementation of Protocol Version 4 (cont.)

The MRI scan should be performed 7–14 days prior to the lumbar puncture to allow time for re-scanning if the quality of the initial MRI is inadequate.

- r The C-SSRS will be used to assess eligibility for the study (full version at *screening*, requiring approximately 20 minutes to administer) and to monitor the patients throughout the study at clinic visits (follow-up version, requiring approximately 5 minutes to administer, assuming absence of suicidal ideation and no change in clinical status from previous administration).
- s The cUHDRS is a composite motor, cognitive, and global functional clinical outcome measure in patients with HD comprised of the TFC, the TMS, the SDMT, and the SWR scores.
- t The electronic devices for remote data collection will be supplied to patients at screening and must be returned to the clinic in cases where the patient does not meet eligibility criteria, at the end of the study, or upon early termination from the study.

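### Two rows of the laboratory severity scale in Appendix 5 (proteinuria and hyperuricemia) give no grade to their highest values

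*Protocol*

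**What the plan says.** Section 5.3.3 states: "Laboratory values determined as an adverse event should be graded as per Appendix 5". Section 6.7 repeats the instruction and then plans adverse event incidence by severity.

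Appendix 5 grades adult proteinuria as follows:
- **Mild:** "1+ proteinuria; urinary protein <1.0 g/24 hrs"
- **Moderate:** "2+ proteinuria; urinary protein 1.0 - 3.4 g/24 hrs", with a protein/creatinine (P/C) ratio of 0.5 to 1.9 as a further criterion
- **Severe:** "Urinary protein ≥3.5 g/24 hrs; Urine P/C >1.9"

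It grades hyperuricemia as follows:
- **Mild:** ">ULN - 10 mg/dL (0.59 mmol/L) without physiologic consequences"
- **Moderate:** no entry
- **Severe:** ">ULN - 10 mg/dL (0.59 mmol/L) with physiologic consequences"

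Section 4.5.6 describes the urine work-up as "Urinalysis, including dipstick (pH, specific gravity, glucose, protein, ketones, blood) and microscopic examination", with microscopy reserved for abnormal dipsticks. Footnote o of the Appendix 1 schedule gives the same content. Neither lists a 24-hour collection or a P/C ratio. Uric acid belongs to the routine serum chemistry panel (section 4.5.6; Appendix 1, footnote m).

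**The concern.** A severity scale should give one grade to every result that the trial's own tests can return. The proteinuria row uses the dipstick for its two lower grades and drops it for the highest. The hyperuricemia row separates Mild from Severe only by physiologic consequences and closes both at the same upper bound, so the row is empty exactly where values are most extreme.

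Investigators assign severity when they record an event, so grades that differ between raters at about 90 sites (section 9.4) are hard to repair after database lock. Proteinuria has some relevance here. Section 5.1.2.4 lists kidney effects as a potential risk and reports one case of moderate proteinuria, considered drug-related, in the open-label study. The renal row of Table 3 uses only eGFR, creatinine clearance and creatinine, so Appendix 5 is the only place in the protocol that gives proteinuria severity levels.

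**Working it through.** The plan states no figure to reproduce. The check applies the Appendix 5 cells as written and looks for values that fall in none of them.

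**Proteinuria, dipstick.** Inputs are the three adult cells quoted above. Levels 3+ and 4+ are assumed to be reportable, since the protocol does not give the dipstick's range.

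| Dipstick | Grade |
|---|---|
| 1+ | Mild |
| 2+ | Moderate |
| 3+ | none |
| 4+ | none |

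**Proteinuria, quantitative.** A 24-hour protein of 0.5 g is Mild, 1.0 g and 3.4 g are Moderate, and 3.5 g and 5 g are Severe. A P/C ratio of 0.5 or 1.9 is Moderate and 2.5 is Severe. So Severe exists on these two measures, but neither is scheduled. Two smaller gaps also appear: 24-hour protein between 3.4 and 3.5 g, and a P/C ratio below 0.5.

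**Hyperuricemia.** The rule as written is: if ULN < value ≤ 10 mg/dL, then Mild without and Severe with consequences; otherwise no grade. The protocol does not give the ULN, so 6, 7 and 8.5 mg/dL were tried. All three give the same result.

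| Uric acid (mg/dL) | Without consequences | With consequences |
|---|---|---|
| 9 | Mild | Severe |
| 10 | Mild | Severe |
| 10.1 | none | none |
| 12 | none | none |
| 15 | none | none |

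**Is the 10 mg/dL bound a unit slip?** 10 mg/dL is 100 mg/L. With an assumed molar mass of 168.11 g/mol, 100 / 168.11 = 0.595 mmol/L, which agrees with the printed 0.59. The bound is therefore not a conversion error.

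**Comparison with the other rows.** Among the rows of Appendix 5 with a numerical Severe cell, hyperuricemia is the only one closed at the extreme end. ALT, AST, creatinine, CPK, potassium and sodium, for example, are all open-ended there. The cells read intact, so text extraction does not explain either gap.

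**The case against.** The strongest reply is that little follows from the gaps, and most of it stands.

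- **Only some values are graded.** Section 5.3.5.5 makes a laboratory abnormality an adverse event only if it has symptoms, a treatment change, an intervention or clinical significance behind it. Appendix 5 also describes its entries as recommendations. A reader might infer that every dipstick above 2+ and every uric acid above 10 mg/dL is affected, in all arms and at all visits. The protocol does not support that.
- **The safety endpoint names another scale.** A reader might take Appendix 5 to be the scale in the first safety endpoint. Section 2.2 points to Table 4, the general scale based on daily activity. Appendix 5 enters only through sections 5.3.3 and 6.7.
- **The data stay visible.** A reader might infer that a treatment-related rise in heavy proteinuria would go unseen. Section 6.7 provides laboratory listings, summaries by treatment and assessment time, and the incidence of marked abnormalities. Section 3.1.2 has the data monitoring committee review laboratory parameters unblinded, about every 6 months. None of this needs an Appendix 5 grade.
- **A grade can still be obtained.** An unscheduled quantitative urine test would give one, and an investigator may simply judge a result severe.
- **The background signal is thin.** The one proteinuria case arose on the Q4W regimen, which is not randomized in this version, and it resolved without intervention. The protocol describes no drug-related uric acid concern.

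These points limit the consequence but do not close the gaps. Table 4 is a poor fallback, because it grades discomfort and disrupted activity, which an asymptomatic laboratory value may not cause, and section 5.3.3 directs such values to Appendix 5.

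**Conclusion.** The defect is real and confined to two rows. In the hyperuricemia row the stated rule gives an illogical result: a patient with consequences loses the Severe grade once uric acid passes 10 mg/dL. This holds for any ULN below 10 mg/dL. In the proteinuria row, Severe cannot be reached from a scheduled test, and a dipstick above 2+ has no grade; the latter rests on the assumption that the laboratory reports such levels.

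The consequence is missing or inconsistent severity labels in the adverse event severity table for events of these two kinds. How many events that would be cannot be derived from the protocol. No efficacy result, sample size, type I error rate or dosing rule depends on these rows. It is a small correction, worth making because it is cheap and because severity is assigned as events are recorded.

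**What to change.** Amend the two rows so that every value the scheduled tests can return has exactly one grade:

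1. **Hyperuricemia:** remove the 10 mg/dL upper bound from the Severe cell, and state the category for values above 10 mg/dL without physiologic consequences.
2. **Proteinuria:** assign each dipstick protein level that the laboratory reports above 2+ to a named category.

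The sponsor should choose the cut-points from the CTCAE version 5.0 source that Appendix 5 cites; none is proposed here. The two small quantitative proteinuria gaps can be closed in the same edit. The cost is two table rows, with no new sampling or visits.
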